5. METHODS

5.1. Assessment of Demographic and Physical Characteristics

A personal information form was used to obtain demographic data. Body height and mass were measured using standard procedures.

5.2. Assessment of Muscle Contractile Properties (TMG)

Muscle contractile properties were assessed using tensiomyography (TMG-BMC Ltd., Ljubljana, Slovenia) on the vastus medialis muscle of the dominant leg. Participants were positioned in supine with the knee supported at approximately 30° of flexion. The muscle belly was identified by palpation, and surface electrodes were placed proximal and distal to the motor point. The measurement probe was positioned perpendicular (90°) to the skin surface. Electrical stimulation was incrementally increased until maximal radial displacement of the muscle was obtained. Participants were instructed to keep their muscles fully relaxed throughout the measurements (Macgregor et al., 2018; Rey et al., 2012; Šimunič, 2012).

The following TMG parameters reflecting muscle contractile properties were analyzed: maximal radial deformation (Dm), contraction time (Tc), and delay time (Td). These parameters have been reported to demonstrate high relative reliability, with intraclass correlation coefficients of 0.97 for Dm, 0.92 for Tc, and 0.86 for Td, along with low measurement error ($CV \approx 2.7$ – 4.7%) (Loturco et al., 2016; Tous-Fajardo et al., 2010). All

measurements were performed before the exercise protocol and within 90 seconds following completion of the final repetition.

5.3. TMG Measurement Reliability

Prior to the main experimental sessions, test–retest measurements were performed on 12 participants with a 48-hour interval. Reliability was assessed using the intraclass correlation coefficient [ICC(3,1)] calculated with a two-way mixed-effects model. ICC values for TMG parameters were 0.91 for Dm, 0.88 for Tc, and 0.83 for Td, indicating high reliability. The standard error of measurement (SEM) and minimal detectable change (MDC95) were calculated to quantify measurement error. SEM and MDC95 values were 0.31 mm and 0.86 mm for Dm, 0.49 ms and 1.36 ms for Tc, and 1.17 ms and 3.24 ms for Td, respectively.

5.4. Assessment of Foot Progression Angle

Habitual FPA values were assessed during dynamic gait analysis using a baropodometric walkway platform (BTS P-Walk, BTS Bioengineering, Italy; 2.4 m). Measurements were performed under standardized laboratory conditions. Participants were instructed to walk across the platform at their natural walking speed, and data collection was initiated without prior notification to preserve the naturalness of the gait pattern. FPA values were automatically calculated by the device's integrated software as the angle between the longitudinal axis of the foot and the direction of progression during gait. FPA values for both feet were obtained separately. A minimum of three valid walking trials were collected per participant, and mean FPA values across trials were used in analyses (Caravaggi et al., 2017; Kawai et al., 2019).

5.5. FPA Measurement Reliability

Test–retest reliability of FPA measurements was assessed in 12 participants with a 48-hour interval. The two-way mixed model intraclass correlation coefficient (ICC 3,1) was 0.92. The minimal detectable change (MDC95) was calculated as 1.8°.

5.6. Leg Press Foot Positioning and Exercise Protocol

In the neutral protocol, participants' feet were placed on the platform at shoulder-width apart with foot rotation in a neutral (0°) position. In the toe-out protocol (30°), feet were placed at the same shoulder-width distance with the forefoot rotated 30° outward. Foot positions were measured using a standard goniometer at each session and verified by angle markings drawn on the footplate (Da Silva et al., 2008; Escamilla et al., 2001; Martín-Fuentes et al., 2020).

All procedures were performed on a 45° inclined leg press machine (Technogym, Italy). Range of motion was restricted from 90° of knee flexion to full extension. One-repetition maximum (1RM) values were determined 48 hours prior to the experimental sessions.

In the experimental session, participants performed the leg press exercise following a standardized general warm-up. The exercise protocol consisted of 2 × 15 repetitions at 40% 1RM followed by 4 × 10 repetitions at 75–80% 1RM. Inter-set rest was standardized at 2 minutes. Tempo was controlled using a metronome with a 2-second eccentric phase and 1-second concentric phase, and technical compliance was monitored by an experienced coach (Ratamess et al., 2009; Nuzzo et al., 2024).

5.7. Outcome Variables

All outcome variables were determined from tensiomyographic (TMG) parameters obtained from the vastus medialis muscle of the dominant leg before the leg press exercise protocol and within 90 seconds following completion of the final repetition. Pre- and post-exercise

measurements were analyzed using raw data within a repeated measures model. Outcome variables were defined a priori.

Primary Outcomes: Changes in Dm and Tc. It was hypothesized that the acute effect of the potential interaction between foot rotation position and habitual FPA phenotype on muscle contractile dynamics would be most evident through Dm and Tc parameters. Accordingly, the Protocol \times Time interaction was evaluated primarily in terms of changes in Dm and Tc.

Secondary Outcomes: Change in the Td parameter.

6. STATISTICAL CONSIDERATIONS

Statistical analyses were performed using SPSS software (Version 27, IBM Corp., Armonk, NY, USA). Descriptive statistics are presented as mean \pm standard deviation (mean \pm SD) and the significance level was set at $\alpha = 0.05$. Normality of continuous variables was assessed using the Shapiro–Wilk test and homogeneity of variance was evaluated with Levene’s test.

To assess potential carry-over effects associated with the crossover design, pre-exercise measurements obtained prior to the second session were compared using paired samples t-tests within each group; no significant carry-over effect was observed (all $p > 0.05$).

A 2 (Group: HFPA vs. NFPA) \times 2 (Protocol: congruent vs. incongruent) \times 2 (Time: pre vs. post) factorial repeated measures ANOVA were applied to examine changes in muscle contractile parameters. Group was included as a between-subjects factor, while protocol and time were included as within-subjects factors. Main effects and all two-way (Group \times Protocol, Group \times Time, Protocol \times Time) and three-way (Group \times Protocol \times Time) interactions were evaluated. As each within-subject factor had two levels, the sphericity assumption was automatically satisfied and no correction was applied.

Primary outcome variables were defined a priori as Dm and Tc. In line with the primary hypothesis of the study, the Protocol \times Time interaction was prioritized during analysis and interpretation.

Where significant main effects or interactions were identified, pairwise comparisons were conducted with Bonferroni correction. Additionally, 95% confidence intervals for mean differences were calculated and reported for all post-hoc comparisons.

Effect sizes were reported as partial eta squared (η^2) and interpreted as small (0.01), medium (0.06), and large (0.14) (Richardson, 2011). The Td parameter was treated as a secondary outcome variable and only significant effects are reported.

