3. STUDY DESIGN

This study was designed as a mixed-design, crossover experimental investigation. In the study design, FPA phenotype (high FPA vs. normal FPA) was defined as the between-subjects factor, while foot rotation protocol (0° neutral vs. 30° toe-out) and time (pre-exercise vs. post-exercise) were defined as within-subjects factors.

All participants were assessed in two separate sessions, each involving one of the two foot rotation protocols, with a 48-hour washout period applied between sessions to minimize potential fatigue and carry-over effects. Within the crossover design, protocol order was fixed on a group-specific basis to minimize learning effects. Accordingly, each group performed the condition congruent with their habitual foot progression angle in the first session and the incongruent condition in the second session.

Pre-exercise TMG values obtained prior to the second session were compared with baseline measurements to confirm return to baseline levels. All experimental procedures were conducted under controlled environmental conditions (24°C) and within the same time-of-day window for each participant (± 1 hour). Participants were instructed to avoid strenuous physical activity and caffeine consumption for 48 hours prior to each measurement.

To minimize measurement bias, the researcher conducting TMG assessments was blinded to participants' phenotype group and the exercise condition applied (single-blind). Exercise administration and data analysis were performed by different researchers, and group codes were anonymized during the analysis process.

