4.5. Sample Size Calculation

Sample size was calculated using G*Power 3.1.9.7 software based on a repeated measures mixed-design ANOVA model (within-between interaction). Effect size estimation was based on tensiomyographic changes reported in the lower extremity muscles following acute resistance exercise. Previous studies have reported large effect sizes (Cohen's $d \approx 1.0$ – 1.9) particularly for Tc and Td parameters (Beato et al., 2021). Adopting a more conservative approach, a medium-to-large effect size ($f = 0.40$) was assumed. With a significance level of $\alpha = 0.05$, statistical power of $(1-\beta) = 0.80$, and a correlation between repeated measures of $r = 0.50$, the minimum total sample size was calculated as 20 ($n = 10$ per group). Considering the within-subject comparison advantage of the crossover design and to compensate for potential data loss, 12 participants were included in each group.

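### Non-significant paired t-tests with 12 per group cannot confirm return to baseline, and resting values do not test carry-over of the exercise response

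*Protocol*

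**What the plan says.** Protocol section 3 sets a 48-hour washout and gives the purpose of the check: "Pre-exercise TMG values obtained prior to the second session were compared with baseline measurements to confirm return to baseline levels".

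Section 6 gives the method and the result together: the resting values before session 2 were "compared using paired samples t-tests within each group; no significant carry-over effect was observed", with all p-values above 0.05. Section 4.5 gives the size of each test: "12 participants were included in each group".

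No equivalence margin, confidence interval or detectable shift is stated for this check. The 95% confidence intervals in section 6 are promised for post-hoc comparisons only.

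Two other statements bear on the point. Section 3 fixes the order so that both groups take the congruent condition first and the incongruent condition second. Sections 5.7 and 6 give priority to Protocol × Time, that is, to the difference between conditions in the pre-to-post change.

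**The concern.** There are two separate problems.

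The first is the inference. A paired t-test asks whether a zero mean shift can be rejected. Failing to reject zero is compatible with no shift and also with a modest shift that 12 pairs are too few to show. Section 3 nevertheless gives confirmation as the purpose.

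The second is the target, and it matters more for the primary result. The check looks only at resting values. Protocol × Time already subtracts each session's own pre-exercise value, so a residual shift that is equal before and after exercise drops out. What would bias the contrast is a different response to the bout in session 2, for instance because the first bout changed how the muscle reacts. Comparing resting values cannot show this. Because every participant took the incongruent condition second, such a change would appear as a Protocol × Time effect. A reader may take the carry-over sentence in section 6 as reassurance on a question that was not examined.

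**Working it through.** **Inputs.** Section 5.3 gives SEMs of 0.31 mm (Dm), 0.49 ms (Tc) and 1.17 ms (Td); MDC95 of 0.86 mm, 1.36 ms and 3.24 ms; and ICCs of 0.91, 0.88 and 0.83. They come from a 48-hour retest, the same interval as the washout. Each test has n = 12 (section 4.5) and α = 0.05 (section 6). The protocol does not state sidedness; two-sided is assumed.

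**Step 1: reproduce the protocol's own figure.** MDC95 = 1.96 × √2 × SEM gives 0.859 mm, 1.358 ms and 3.243 ms. These match section 5.3, so SEM × √2 can serve as the SD of a between-session difference: 0.438 mm, 0.693 ms and 1.655 ms. The protocol states no power or detectable shift for the carry-over test, so there is no figure to reproduce there.

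**Step 2: detectable resting shift.** For a two-sided paired t-test with n = 12 (11 degrees of freedom), 80% power needs a mean shift of 0.889 SDs of the difference. The between-person SD is SEM / √(1 − ICC).

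| | Dm | Tc | Td |
|---|---|---|---|
| 0.889 × SD of difference | 0.39 mm | 0.62 ms | 1.47 ms |
| Between-person SD | 1.03 mm | 1.41 ms | 2.84 ms |
| Shift as share of that SD | 0.38 | 0.44 | 0.52 |
| Shift as share of MDC95 | 0.45 | 0.45 | 0.45 |
| Power for a shift of half a between-person SD | 96% | 90% | 77% |

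A shift of one SEM is 1/√2 = 0.707 SDs of the difference and is detected with 61% power. A shift of half an SD of the difference is detected with 35% power.

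**Step 3: can an interval rule work with these numbers?** Take a margin of ±1 SEM (0.707 SDs of the difference), a 90% CI and a true shift of zero.

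- Per group, n = 12: the expected half-width is 1.796 / √12 = 0.518 SDs of the difference, which is 0.23 mm, 0.36 ms and 0.86 ms. All are inside the margin, but the estimate itself also varies. By simulation the whole interval lies inside the margin only 49% of the time.
- Pooled, n = 24: the half-width is 1.714 / √24 = 0.350 SDs of the difference, which is 0.15 mm, 0.24 ms and 0.58 ms. By simulation the interval lies inside the margin 91% of the time.

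**Step 4: what the check can see.** Write a resting shift in session 2 as c, added equally to the pre and post values. The session-2 change is (post + c) − (pre + c) = post − pre, so c cancels. Now let the session-2 response itself change by r. Session 2 is the incongruent condition for all 24 participants, so Protocol × Time estimates the protocol effect plus r. The resting comparison contains c but not r, and no participant took the conditions in the other order from whom r could be separated.

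**The case against.** The strongest reply is that the resting check is not weak on the protocol's own scale. With these ICCs a shift of half a between-person SD would be found with 96% (Dm), 90% (Tc) and 77% (Td) power, and a mean shift as large as MDC95 almost surely. This stands. A reader might infer that the tests would miss large residual shifts, and the protocol's figures do not support that. The 35% figure refers to half an SD of the difference, about 0.71 SEM, which is smaller than the ±1 SEM margin suggested below. It is not evidence that important shifts go unseen. Under the planning correlation of 0.50 in section 4.5 the power for half a between-person SD would also be 35%, but the measured 48-hour reliability in section 5.3 is the more direct guide.

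A reader might also infer that this check is the only protection against carry-over. It is not. Section 3 also sets the 48-hour washout, the same time of day, a controlled temperature, limits on strenuous activity and caffeine, and a blinded TMG assessor. These reduce the risk, but they do not measure it or remove an order effect.

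Section 6 reports no significant effect, which is literally a test result and not a claim of no effect. The overreach arises when it is read with the purpose stated in section 3.

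Finally, the untested session-2 response stems from the fixed order, not from the t-test, and no re-analysis of resting values can repair it. That is correct. What can still be corrected is the text, which should not let a resting-value test stand as an answer on the response.

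**Conclusion.** The concern holds in a limited form. Non-significance with 12 per group does not confirm return to baseline: shifts below about 0.39 mm, 0.62 ms and 1.47 ms are not reliably excluded, and a shift of one SEM would go undetected about 39% of the time (100% − 61%). These shifts are moderate, not large. Since a constant shift cancels in Protocol × Time, missing one would do little to the prioritised contrast. The more serious limit is that carry-over or period effects on the response were not tested and, with the order fixed, cannot be separated from Protocol.

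None of this shows that carry-over occurred or that the primary result is wrong; the protocol gives no data from which to judge that. The figures assume two-sided tests, approximately normal differences, and that the SEMs from 12 reliability participants apply to the main sessions. If the between-session differences were more variable, the detectable shifts would be larger.

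**What to change.** 1. Replace the p > 0.05 rule with the mean session-2-minus-session-1 pre-exercise difference and its 90% CI for Dm, Tc and Td. Give it per group as description and pooled over the 24 participants. The per-group values should stay visible because opposite shifts in the two groups would cancel when pooled.
2. Claim return to baseline only if the pooled interval lies within a stated margin, for example ±1 SEM (0.31 mm, 0.49 ms, 1.17 ms). Label the margin as post hoc, because the test results are already reported. Otherwise write that a residual shift is not excluded. Do not apply the rule per group: with no true shift it would pass only about half the time.
3. Change the wording on confirmation in section 3 to match.
4. State in section 6 that carry-over or period effects on the exercise response were not tested and cannot be separated from the Protocol effect under the fixed order.

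The cost is a short re-analysis of existing data, a few sentences, and a carry-over statement that may be weaker than the present one.

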2.2. Hypotheses

Primary hypothesis: When the foot rotation position applied during exercise is incongruent with the individual's habitual foot progression angle, the contractile responses of the vastus medialis muscle would be more pronounced.

Secondary hypothesis: A neutral foot position in individuals with a habitually high FPA profile, and an externally rotated foot position in individuals with a normal FPA profile, would be associated with greater contractile responses.

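### The prioritised Protocol × Time contrast compares the foot-angle response between two non-randomised phenotype groups and also carries the whole session effect, so it supports an association, not an effect of congruence

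*Protocol*

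**What the plan says.** The protocol defines the Protocol factor in two ways. Section 3 states that "foot rotation protocol (0° neutral vs. 30° toe-out) and time (pre-exercise vs. post-exercise) were defined as within-subjects factors". Section 6 labels the same factor "Protocol: congruent vs. incongruent" and adds that "Group was included as a between-subjects factor, while protocol and time were included as within-subjects factors". Sections 5.7 and 6 both give priority to Protocol × Time, for Dm and Tc.

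The secondary hypothesis in Section 2.2 shows which angle is expected to give the larger response in each group: "A neutral foot position in individuals with a habitually high FPA profile, and an externally rotated foot position in individuals with a normal FPA profile". So incongruent means 0° in the high-FPA (HFPA) group and 30° in the normal-FPA (NFPA) group. Section 3 also fixes the order: "each group performed the condition congruent with their habitual foot progression angle in the first session and the incongruent condition in the second session".

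Section 4.4 forms the groups by measured FPA (above 13°, or 0° to 13°), with 12 athletes in each.

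The model in Section 6 names no covariate. Suitable data exist: Section 5.1 records demographics and says "Body height and mass were measured using standard procedures", and Section 5.6 says "One-repetition maximum (1RM) values were determined 48 hours prior to the experimental sessions".

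**The concern.** A reader of Section 6 sees Protocol listed as a within-subjects factor and may take each athlete to be his own control for congruence. He is his own control for foot angle only. Each athlete has one congruent angle, fixed by his phenotype, so congruence can be separated from angle only by comparing the two phenotypes.

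The phenotypes were not allocated. Any trait that differs between the groups and changes how a person responds to toe-out would be read as an effect of congruence. The fixed order adds a second problem: anything that makes the response in session 2 differ from that in session 1 is also read as congruence.

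The primary objective in Section 2.1 speaks of effects of the interaction between foot position and phenotype. What is at stake is whether a significant result can carry that wording.

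**Working it through.** The protocol gives no figure for this point, so there is none to reproduce. The sample size in Section 4.5 is unaffected, because recoding the factor leaves F and its df unchanged.

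**1. What the contrast estimates.** For each athlete let θ = (post−pre at 30°) − (post−pre at 0°), and let C = incongruent change − congruent change.

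- NFPA (incongruent = 30°): C = +θ.
- HFPA (incongruent = 0°): C = −θ.
- Protocol × Time averages C over two equal groups: ½[mean θ(NFPA) − mean θ(HFPA)].

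This is half the Group × Angle × Time contrast. A numerical check on simulated data with 12 per group gave F = 0.8562 under both codings, with 24 − 2 = 22 error df.

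Under the Section 3 coding (0° vs 30°), Protocol × Time would be a different quantity: the within-person angle effect averaged over groups. The phenotype comparison would then be the three-way term.

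**2. Trait confounding (assumed inputs).** Suppose there is no true phenotype effect. A trait correlates c with θ and differs systematically by d SD between groups. With θ in SD units:

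- Bias in the group difference is c·d; bias in Protocol × Time is ½·c·d.
- The standard error of the group difference is √(2/12), so the noncentrality is c·d/√(2/12) = c·d·√6.
- Example: c = 0.5, d = 0.8 gives 0.5 × 0.8 × 2.449 = 0.98.

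| c | d | Two-sided rejection rate, nominal 5%, 22 df |
|---|---|---|
| 0.3 | 0.5 | 6.4% |
| 0.5 | 0.5 | 9.0% |
| 0.5 | 0.8 | 15.5% |
| 0.5 | 1.0 | 21.6% |
| 0.7 | 1.0 | 37.5% |

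Only a systematic difference inflates the rate. With c = 0.5 and d = 0, simulation gave 4.9%, so chance imbalance is already covered by the test.

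**3. Which adjustment works.** In simulation at c = 0.5, d = 1.0:

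- A covariate with one common slope in the congruence-coded model left the bias at 0.256, the same as without it.
- Letting the covariate act on the actual angle response, which is what regressing θ on Group and the covariate does, cut the bias to 0.005 and the rejection rate to 4.9%.

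The common slope fails because C reverses the sign of θ in one group.

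**4. Session effect (assumed inputs).** Let session 2 differ from session 1 in response by s SD of C, with no other effect. Both groups do the incongruent condition second, so the contrast is shifted by the full s. In the model for θ, the Group coefficient is shifted by 2s, because 30° comes second in NFPA and first in HFPA. The noncentrality is s·√24; for s = 0.25 it is 0.25 × 4.899 = 1.22.

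| s | Unadjusted, simulated | With the covariate acting on angle, simulated |
|---|---|---|
| 0.25 | 0.21 | 0.20 |
| 0.50 | 0.65 | 0.63 |
| 0.75 | 0.94 | 0.93 |

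A session shift of a quarter SD thus raises the rejection rate as much as a 1.0 SD trait imbalance with correlation 0.5 (noncentrality 0.5 × 1.0 × 2.449 = 1.22). Adjustment does almost nothing about it.

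The carry-over check in Section 6 does not settle this. It compares pre-exercise values, that is, levels, whereas the contrast concerns pre-to-post changes.

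**The case against.** Several points on the other side stand.

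- **The sentence on factor roles is correct.** Protocol and Time do vary within each athlete. A reader might infer that the test is invalid or has the wrong error term. It is not and does not: F and df are the same under either coding.
- **The protocol does not claim protection from confounding.** A reader might take "Considering the within-subject comparison advantage of the crossover design" in Section 4.5 as such a claim. It appears in the sample-size argument and concerns precision. That section also names a within-between interaction, so the between-group element is acknowledged.
- **Missing covariates are not in themselves an error.** Covariate choice and sensitivity models may sit in a statistical analysis plan that is not shown, and phenotype cannot be randomised in any study.
- **The design already narrows some differences.** All athletes are male competitive bodybuilders aged 20 to 35 (mean 27.5, SD 3.76) with at least five years of training, and load is set as a percentage of individual 1RM. Nothing in the documents shows that age or relative strength changes the response to toe-out.
- **All sizes are assumed.** The low end, 6%, is close to nominal.

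One further inference must be resisted: that agreement between adjusted and unadjusted estimates would justify causal wording. Both carry the same session shift and the same unmeasured traits, so they can agree on a biased value.

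None of this changes what the prioritised contrast estimates. The model, the coding, the order and the prioritised test are all fixed in the protocol itself.

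**Conclusion.** The point holds as one of interpretation. With the Section 6 coding, Protocol × Time is exactly half the between-phenotype difference in the 30°−0° response, plus the full difference in response between sessions. That follows from the protocol's own definitions and needs no assumption beyond the mapping of angle to congruence in Section 2.2.

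The test is valid as a test of that quantity. It cannot by itself attribute the quantity to congruence.

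The size of any bias is unknown from the documents. The 6% to 37% range rests on the assumed imbalances and correlations and on there being no session effect; the session figures rest on assumed shifts. Of the two sources, the session effect is probably the more serious, because no covariate removes it. Adjustment for measured traits is a cheap partial safeguard and not a cure.

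**What to change.** 1. Reconcile the definition of Protocol in Section 3 (0° vs 30°) with that in Section 6 (congruent vs incongruent). State which interaction answers the primary hypothesis under the definition kept. If the congruence coding stays, say that Protocol × Time is the Group × Angle × Time contrast re-expressed.
2. Add one sensitivity model each for Dm and Tc. With D = (post−pre at 30°) − (post−pre at 0°), fit D ~ Group + 1RM per kg body mass (and age). Report the Group coefficient with its 95% confidence interval beside the unadjusted one. Do not substitute a common-slope covariate in the congruence-coded ANOVA.
3. Tabulate these covariates by phenotype group.
4. Label the model post hoc if data have been seen. Section 6 already reports the outcome of the carry-over check, so this is likely.
5. Word the conclusion as an association with FPA phenotype, confounded with session order, whether or not the two estimates agree.

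The cost is one extra model per primary outcome on data already collected, and one or two of the 22 error df. Unmeasured traits and the session effect remain.

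### No rule joins the two primary outcomes, so if either Dm or Tc may carry the single primary hypothesis, its false-positive rate is about 7% to 9.75% and not 5%

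*Protocol*

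**What the plan says.** Protocol section 2.2 gives one primary hypothesis: contractile responses of the vastus medialis are larger when foot position does not match the habitual angle. It does not say which parameter shows this.

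Section 5.7 lists two: "Primary Outcomes: Changes in Dm and Tc". Section 6 repeats that "Primary outcome variables were defined a priori as Dm and Tc", sets a single significance level of 0.05, and says of Protocol × Time that the "interaction was prioritized during analysis and interpretation". Each outcome therefore has its own 2 × 2 × 2 ANOVA and its own Protocol × Time test.

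The only multiplicity correction in section 6 is Bonferroni, for pairwise comparisons once a main effect or interaction is significant. No text combines Dm and Tc, orders them or divides alpha between them.

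Section 4.5 gives one calculation, at alpha 0.05 and power 0.80 with correlation 0.50, in which "a medium-to-large effect size ($f = 0.40$) was assumed". It arrives at 20 participants, and 24 were enrolled. It names no outcome.

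**The concern.** Two tests at 0.05 decide one hypothesis. Under the text as written, support could be declared on Dm alone, on Tc alone or on both. The Bonferroni step cannot help, because it acts within one outcome and only after that outcome's interaction test has already been passed.

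Two things are at stake. The primary claim may carry a false-positive rate well above the stated 5%. And if Dm and Tc disagree, the protocol offers no agreed reading, so the result can be interpreted either way after it is seen. This remains true even if every other term in the ANOVA is treated as exploratory.

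**Working it through.** **Inputs.** Two primary outcomes (sections 5.7 and 6); alpha 0.05 (sections 4.5 and 6); f = 0.40, r = 0.50, power 0.80, calculated N = 20, enrolled N = 24 in two groups of 12 (section 4.5). Not given: the Dm–Tc correlation, the number of measurements m in the sample-size model, and the effect-size convention. These are treated as assumptions.

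**1. The plan's own sample size.** For a within-between interaction with two groups under the G*Power default convention, λ = f²·N·m/(1 − r), df1 = m − 1 and df2 = (N − 2)(m − 1).
- m = 2: λ = 0.16 × 2 × N/0.5 = 0.64N. N = 14 gives 78.5% power and N = 16 gives 84.5%, so the minimum is 16. N = 20 gives 92.2%.
- m = 4: λ = 1.28N. The minimum is 12 (88.3%).

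The stated 20 is not reproduced on either reading. It does appear at m = 2 with 90% power, or at m = 4 with r = 0 (83.7%). The power figures below are therefore given on two bases.

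**2. Error across the two tests.**
- Either outcome suffices, independent tests: 1 − (1 − 0.05)² = 0.0975.
- Either outcome suffices, correlated tests: simulated with 24 participants, 22 error df and 100,000 runs per correlation (Monte Carlo error about 0.1 percentage point).

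| Correlation of the two contrasts | Familywise error |
|---|---|
| 0 | 9.6% (exact 9.75%) |
| 0.3 | 9.5% |
| 0.5 | 8.9% |
| 0.7 | 8.4% |
| 0.9 | 6.9% |
| 1.0 | 5.0% |

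Repeat simulations differ by up to about 0.3 points (for example 6.9% to 7.2% at 0.9).
- Both outcomes required at 0.05: at most 5%.
- Each outcome tested at 0.025: 1 − 0.975² = 4.94% if independent, and never above 5%. Holm has the same 5% ceiling.

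**3. What control costs in power.** Under Holm the smaller p-value is judged at 0.025 and, if it passes, the other at 0.05. Power at 0.025 is therefore a floor for each outcome.

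| Basis | N | One outcome at 0.05 | One outcome at 0.025 | Both at 0.05, independent |
|---|---|---|---|---|
| f = 0.40, r = 0.50, m = 2 (λ = 0.64N) | 20 | 92.2% | 86.0% | 0.9224² = 85.1% |
| same | 24 | 96.3% | 92.6% | 0.9627² = 92.7% |
| 80% at N = 20 taken at face value (λ = 8.78) | 20 | 80.0% | 69.6% | 0.80² = 64.0% |
| same, scaled to the enrolled sample (8.78 × 24/20 = 10.53) | 24 | 87.3% | 79.3% | 76.2% |

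Positive correlation raises the last column. A stricter convention, λ = 0.32N with 1 df, gives 75.5% for a single outcome at 0.05 with N = 24. On that reading the target is missed before a second outcome is considered.

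**The case against.** The best defence has three parts.

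First, rules for combining primary outcomes are often left to a statistical analysis plan, and section 6 never claims familywise control. This stands only in part. Section 6 does fix the primary outcomes, the prioritised term, the alpha and the scope of the correction, and that scope leaves out the two tests that decide the hypothesis.

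Second, Dm and Tc come from the same assessment of one muscle (section 5.2), so independence is an upper bound and a doubled error rate is the extreme case. This stands, and it is why a range is given. The excess disappears only as the correlation approaches 1.

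Third, a reader might infer a dilemma: if the 5% error is kept, the 80% power must be lost, with power falling to about 70% per outcome or to 64–75% for both. The documents do not support that. Those figures put exactly 80% power at 24 participants, whereas section 4.5 attaches 80% to 20 and then enrols 24. On the document's f and r with two measurements, power at 24 stays above 92% under either rule. Taking 80% at 20 at face value, the shortfall at 24 is small: 79.3% at 0.025, and 76.2% or more for both. Section 4.5 also sizes a within-between interaction, whereas Protocol × Time, with protocol coded congruent or incongruent, is purely within-subject. Its 80% is therefore not a stated power for the prioritised test. That mismatch is a separate matter.

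**Conclusion.** The point holds for error control. Nothing in the protocol controls error across the two Protocol × Time tests that decide the single primary hypothesis. If either outcome may carry the claim, the familywise error is about 7% (correlation 0.9) to 9.75% (independent tests). It is held to 5% if both are required, which the protocol does not say. These figures assume both null hypotheses are true and each test is at 0.05.

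It does not hold as a claim that 80% power necessarily fails. Section 4.5 does not say whether its 80% refers to one outcome, either or both, and its sample size cannot be reproduced without assumptions about m and the convention.

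Nor do the documents show that support was actually declared on one outcome. Section 6 is in the past tense and already reports the carry-over comparison, but gives no post-exercise results. This should be fixed, and it is inexpensive to fix.

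**What to change.** In section 6, add:

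> The primary family is the Protocol × Time test for Dm and for Tc. The two p-values are Holm-adjusted, and the primary hypothesis is supported only for an outcome whose adjusted p is below 0.05. If only one is significant, the conclusion is limited to that outcome.

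The last sentence settles discordant results. If Dm and Tc results had been seen before the rule was written, label it as added post hoc.

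In section 4.5, state that the calculation is for one outcome at 0.05. Then give the power at 0.025 for N = 24, with the number of measurements and the effect-size convention used. That is about 93% with f = 0.40, r = 0.50 and two measurements, or about 79% if 80% at N = 20 is taken at face value. The 70% and 64–75% figures should not be inserted.

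The cost is a slightly stricter threshold for the smaller p-value and a slightly lower stated power. No new data are needed.
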